STUDY PROTOCOL

Long-term outcomes of ultrasound-guided percutaneous bilateral cardiac sympathetic denervation in patients with refractory arrhythmic storm: a single-center case series.

code CEImPA 2023.139

Oviedo, April 11, 2023

PROJECT TITLE

Long-term outcomes of ultrasound-guided percutaneous bilateral cardiac sympathetic denervation in patients with refractory arrhythmic storm: a single-center case series.

BACKGROUND AND CURRENT STATE OF THE ARTS

Electrical storm (TS) or constant ventricular tachycardia is a life-threatening condition associated with high morbidity and mortality. It is defined as three or more sustained events of ventricular tachycardia (VT) or ventricular fibrillation within a 24-hour period, with or without implantable cardioversion-defibrillation (ICD) therapy [1-2], with a prevalence of 10%–25% in patients with ICDs.

If left untreated, TS can lead to left ventricular systolic dysfunction, which can progress to heart failure [3]. Treatment includes the use of antiarrhythmic drugs to suppress ventricular arrhythmias (VAs), ICD reprogramming, and antitachycardia pacing techniques. In some complex cases, urgent catheter ablation may be necessary to treat VAs and TS. However, these conditions are sometimes refractory to standard medical therapies. In these cases, neuromodulation, which reduces sympathetic efferent tone to the myocardium, can help suppress refractory arrhythmias and can be achieved with a stellate ganglion block (SGB) [4-7], sometimes representing the patient's last option, either as definitive therapy or as a bridge to transplantation.

Although SGB has been shown to be effective in terminating the electrical storm, there is a lack of robust clinical evidence supporting its use, as it is not possible to conduct double-blind randomized trials in this clinical setting. Current evidence comes from small case series reports in the literature [8-13].

At our hospital, a multidisciplinary team of cardiologists, intensivists, and anesthesiologists manages these patients. To date, we have performed numerous SGB with good results. This experience has led to the need for this project, to publish our experience on this topic and contribute to the widespread use of this treatment in the management of these patients.

STUDY HYPOTHESIS

SGB and bilateral cardiac sympathetic denervation (BCSD) produce a sustained cessation of refractory electrical storms.

OBJECTIVES

Primary

- To describe the effectiveness of SGB and BCSD bilateral in patients with advanced heart failure and electrical storm refractory to conventional treatment.

Secondary

- To study the long-term (12 months) temporary effectiveness after performing the technique.
- To describe the characteristics and comorbidities of these patients.
- To describe the complications arising from the techniques.

STUDY METHODOLOGY

DESIGN: A prospective, single-center observational study.

STUDY POPULATION: Patients with advanced heart failure and arrhythmic storm refractory to conservative and ablative medical treatment in the arrhythmia unit of the Central University Hospital of Asturias.

ETHICAL CONSIDERATIONS: The study has been authorized by the Ethics Committee for Research with Medicinal Products of the Principality of Asturias, with code CEImPA 2023.139.

INCLUSION CRITERIA: All patients over 18 years of age diagnosed with arrhythmic storm refractory to conservative medical treatment.

EXCLUSION CRITERIA: Patients with contraindications to perform the interventional technique (active infection at the puncture site and refusal by the patient).

ANALYZED VARIABLES

The primary study outcome was arrhythmic burden, assessed both in the early period (first 24 hours) and in the long term (during the 12 months following BCSD).

Secondary variables included baseline clinical characteristics and comorbidities of the enrolled patients. Procedure-related complications were also recorded, including local hematoma, hoarseness, brachial plexus involvement, respiratory compromise and adverse reactions to the injected substances. In addition, variables related to long-term prognosis were recorded (heart transplantation, and all-cause mortality).

SAMPLE SIZE ESTIMATION: All consecutive cases eligible for this therapy were collected between April 2023 and March 2025.

DATA COLLECTION: A data collection form will be used for the study. The researcher will include the patient sample in it, without any identifying information.

STATISTICAL ANALYSIS

Statistical analyses were performed using the R statistical software package. Continuous variables are expressed as mean \pm standard deviation, and categorical variables as absolute numbers and percentages. Comparisons between groups were performed using Student's t-test for continuous variables (after confirmation of normality) and the chi-square test for categorical variables, with Fisher's exact test applied when chi-square assumptions were not met.

Event-free survival (arrhythmic recurrence, heart transplantation, or mortality) was evaluated using Kaplan–Meier survival analysis.

LIMITATIONS OF THE STUDY: those due to the prospective design of the study and those arising from the impossibility of reviewing the patients included in the study database.

CREDIT AUTHORSHIP CONTRIBUTION STATEMENT:

[name]: Project administration as doctoral thesis, writing – review & editing. [name]: writing – review & editing. [name]: writing – review & editing. [name]: data curation. [name]: data curation. [name]: data curation. [name]: data curation. [name]: review & editing. All authors have read and agreed to the published version of the manuscript.

REFERENCES

6. Meng L, Tseng C-H, Shivkumar K, et al. Efficacy of stellate ganglion blockade in managing electrical storm: a systematic review. *JACC Clin Electrophysiol* 2017;3:942–9.

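### Mean ± SD is the only continuous summary planned, and it is likely to describe the primary outcome, arrhythmic burden, poorly; the named tests refer to groups that this single cohort does not define

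*Combined protocol and SAP*

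**What the plan says.** All references are to the combined protocol and SAP.

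- **Aim (OBJECTIVES, Primary).** The aim is descriptive: "To describe the effectiveness of SGB and BCSD bilateral in patients with advanced heart failure". The title calls the study a case series, and the design is observational with consecutive eligible cases. No comparator or subgroup is set up.
- **Primary outcome (ANALYZED VARIABLES).** "The primary study outcome was arrhythmic burden, assessed both in the early period (first 24 hours) and in the long term", the latter being 12 months after the procedure. Both windows follow the procedure. No unit is given for burden.
- **Continuous summary (STATISTICAL ANALYSIS).** "Continuous variables are expressed as mean" ± standard deviation. No median, range or other summary is mentioned. Categorical variables are given as numbers and percentages.
- **Tests (same section).** "Comparisons between groups were performed using Student's t-test for continuous variables (after confirmation of normality"); chi-square is used for categorical variables, "with Fisher's exact test applied when chi-square assumptions were not met". The groups are not named here or anywhere else. Categorical data have a fallback test; continuous data that fail the normality check have none.
- **Time to event (same section).** "Event-free survival (arrhythmic recurrence, heart transplantation, or mortality) was evaluated using" Kaplan–Meier.
- **Other outcomes (ANALYZED VARIABLES).** "variables related to long-term prognosis were recorded (heart transplantation, and all-cause mortality").

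**The concern.** The main issue is the summary of the primary outcome. The background defines a storm by counting sustained events (at least three in 24 hours), and the hypothesis is that storms cease. If burden is counted in the same way and the procedure works even partly as hoped, many patients will have zero events and a few will have many. Mean ± SD does not show that shape, and it can give an interval that runs below zero for a quantity that cannot be negative. A reader would then learn neither the typical result nor how many patients had no events in the first 24 hours.

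The second issue is the test sentence. A single cohort offers no obvious groups, so nobody can tell what the t-test, chi-square or Fisher test will compare. If a continuous variable fails the normality check, the method has to be chosen after the data are seen. Taken alone these are missing details. They matter because they sit beside a summary that does not suit the outcome.

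**Working it through.** The plan gives no sample size, distribution, effect size or alpha, so it has no figure to reproduce. All numbers below are illustrations on assumed inputs.

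**1. What one distribution looks like under each summary.** Assume a fraction z of patients are certain to have no events after the procedure. The rest follow a negative binomial with mean m = 5 (half an assumed pre-procedure mean of 10) and size k (small k means strong spread).

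- Mean = (1 − z)m
- Variance = (1 − z)(m + m²/k + m²) − mean²
- P(zero) = z + (1 − z)[k/(k + m)]^k

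| Case | Mean | Variance | Mean ± SD | Median [IQR] | Zero events |
|---|---|---|---|---|---|
| z = 0.6, k = 1 | 0.4 × 5 = 2.0 | 0.4 × 55 − 4 = 18 | 2.0 ± 4.2 | 0 [0–2] | 0.6 + 0.4/6 = 67% |
| z = 0.3, k = 5 | 0.7 × 5 = 3.5 | 0.7 × 35 − 12.25 = 12.25 | 3.5 ± 3.5 | 3 [0–6] | 0.3 + 0.7/32 = 32% |
| z = 0, k = 5 | 5.0 | 35 − 25 = 10 | 5.0 ± 3.2 | between 4 and 5 [3–7] | 1/32 = 3% |

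The first row is badly served by mean ± SD, the second less so, and the third hardly at all.

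**2. How often mean minus SD is below zero.** These are simulated samples of n = 10, with m = 2.5, 5 or 10:

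| Certain zeros | k = 1 | k = 5 |
|---|---|---|
| 60% | 96–98% | 91–96% |
| 30% | 86–92% | 38–67% |
| none | 41–63% | 0.1–11% |

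A negative value signals skew and is not an error in itself. The last row shows how far the result depends on the assumed zeros and spread.

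**3. The normality condition.** With 30% or 60% certain zeros, Shapiro–Wilk rejects normality of the post-procedure count in 32–99% of samples at n = 10 and 52–100% at n = 15. A continuous fallback would often be needed if burden were compared between groups.

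**4. Twelve-month burden when death or transplantation ends follow-up.** Assume 20% or 40% leave at a constant hazard, L = −ln(1 − p) = 0.223 or 0.511 per year.

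- Observed time as a fraction of plan is (1 − e^(−L))/L = 0.896 or 0.783. If events occur at a constant rate, a raw count is 10–22% low.
- If event intensity instead halves each month, g = 12 ln 2 = 8.32 per year. The raw count is then about g/(g + L) = 8.32/8.54 = 0.974 or 8.32/8.83 = 0.942 of the full count, only 3–6% low. A rate per observed time would be 0.974/0.896 = 1.09 or 0.942/0.783 = 1.20 of the true rate, 9–20% too high.

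The direction and size of the error therefore depend on when events happen, which the plan does not tell us. One early event also makes a per-patient rate unstable: one event in two days annualises to 365/2, about 180. Follow-up time should be shown, but an annualised rate should not carry the result.

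**5. Precision of a proportion free of events.** For an assumed 80%, exact 95% intervals are 44–97% for 8/10, 52–96% for 12/15 and 61–92% for 24/30. Mean ± SD conveys none of this uncertainty.

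**The case against.** The strongest reply is that this is a descriptive case series with no planned hypothesis test, and that much of the section suits it. That is right in several respects.

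- **A reader might infer that the whole statistical section does not fit one cohort.** The text does not support that. Numbers with percentages and Kaplan–Meier both work for one cohort and can show part of who remained event-free. What they leave open is narrower: the curve is a composite with transplantation and death, it stops at the first event, and no count of patients with zero events at 24 hours is promised.
- **A reader might infer that the plan will test before against after with an unpaired t-test and so overstate benefit.** No such comparison is promised, and a descriptive objective does not need one. If the unpaired test were used on positively correlated before/after data, it would be conservative.
- **A reader might infer a known bias in the 12-month figure.** The plan does not say how burden is expressed when follow-up is short, and the size depends on the timing of events.
- **The skewed-count premise is assumed.** This stands. The event-based storm definition and the cessation hypothesis make it plausible, but the second is the claim under study.

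What survives is the single summary for a primary outcome that probably needs another, and a test sentence with no stated object.

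**Conclusion.** The concern holds as a reporting fault that should be corrected. That mean ± SD is the only continuous summary, that the groups are undefined and that continuous data have no fallback are certain from the text. The size of the harm is conditional. It is large if burden is a count with many zeros or strong overdispersion, as in the 2.0 ± 4.2 against 0 [0–2] case, and small if zeros are few and spread is mild. The cost is clarity about the primary outcome; the documents give no basis for saying that the plan would create a false claim of benefit.

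**What to change.** Replace the continuous-data text for the primary outcome with wording such as:

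> Arrhythmic burden is reported separately for the first 24 hours and for the 12 months after the procedure, as median [IQR] and range. The number and percentage of patients with zero events are given for each window, with an exact 95% CI for the proportion. Deaths, transplantations and follow-up time are shown beside the 12-month figure.

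In addition:

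- State which independent subgroups the t-test, chi-square and Fisher tests compare, and name a non-parametric alternative for continuous data. Otherwise delete the sentence.
- If a before/after comparison is made from counts already recorded, use the Wilcoxon signed-rank test with its estimate and 95% CI, and call the result a before/after change only. The LIMITATIONS section cites "the impossibility of reviewing the patients included in the study database", so if pre-procedure counts were not captured, omit the comparison.
- Keep Kaplan–Meier.
- If data have already been analysed, date the change and say so.

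The cost is slightly more reporting. The descriptive items use the burden data already planned for, and Kaplan–Meier already needs event dates. A median of 0 can hide a few patients with high burden, which is why the range is included.
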